### **5.7.4 12, 24, 36, 48, 60 Months Clinical Follow Up**

All subjects will be contacted for clinical evaluation at 12, 24, 36, 48, 60 months post-procedure ( $\pm$ 30 days), including:

- Assessment of the anginal status (CCS or Braunwald),
- Any adverse, or serious adverse events
- Anti-platelet/anti-coagulant treatment plan

Table 2: Schedule of treatments and assessments-baseline to 12-month follow up

	Baseline	Procedure	Discharge	30 days ± 7days	180 days ±30 days	270days +30 days	12, 24, 36, 48, 60 months ±30 days
Signed informed consent	X						
Inclusion/Exclusion Criteria	X	X					
Pregnancy Screening	X 						
Medical and Cardiac History	X						
Medication		X 	X 	X 	X 	X 	X 
Blood Routine	X 					X	
Infectious diseases screening	X 						
Serum Creatinine	X 		X 			X	
Liver function test	X 		X 			X	
Serum glucose	X 						
Serum lipid	X 						
CK / CK-MB	X 		X 				
Troponin I or T	X 		X 				
Physical examination and/or Ischemic status	X		X	X	X	X	X
Intervention		X					
Angiography		X 				X 	
12-lead ECG	X 		X 			X	

1. For premenopausal women, a pregnancy test must be performed within 72 hours prior to angiography  
 2. Procedure Medication  
 3. Anti-platelet/anti-coagulant medical therapy  
 4. Within 7 days prior to procedure  
 5. Within 72 hours prior to procedure  
 6. Serum Creatinine within 24 hours post-procedure  
 7. Liver function test(ALT, AST) within 24 hours post-procedure  
 8. CK & CK-MB & Troponin within 6-24 hours post-procedure  
 9. Angiography of all procedure steps and Pre- and Post- procedure in two orthogonal views  
 10. Angiography in the same two orthogonal views as at index procedure  
 11. ECG within 6- 24 hours or before discharge

---

## **5.8 Unscheduled Coronary Angiogram Follow Up**

Any unplanned angiography and revascularization must be followed by a full clinical evaluation. The required data is to be entered into the eCRF. All films must be sent to the angiographic core laboratory for review.

- If the subject undergoes a clinically driven angiography within 6 months post procedure, having no re-intervention of the target lesion(s), the subject must return for the angiographic follow up visit, 9 months post procedure.
- If the subject undergoes a clinically driven angiography between 6-9 months post procedure, this will be considered as the 9 months follow up angiography.
- If the subject has a re-intervention for in-stent restenosis at any time prior to the 9 months follow up the subject will not have an additional angiography at the 9 months follow up visit.
- However, if the subject has two treated target vessels with the study stent, whereof only one was re-intervened, the subject must return for the repeat angiography at the 9 months follow up visit. If one had revascularization and in-stent restenosis during 6-9 months, the 9 months follow up visit is not needed.

## **5.9 Treatment Failures**

Failure to implant the study stent at the intended target lesion must be recorded on the Case Report Form as a treatment failure. If possible and feasible, another study stent will be chosen as first choice to treat this lesion.

## **5.10 Additional Stent Treatment**

In the event of a major dissection or an occlusive complication manifested as decreased target vessel flow, chest pain, or ischemic ECG changes after the index procedure, which do not respond to repeat balloon inflations or intracoronary vasodilators (nitroglycerin, verapamil, diltiazem, nitroprusside), other bailout procedures may be performed which may include additional stenting. Should a second stent be used, it must be a study stent unless clinically contraindicated. Multiple stenting with the Orsiro stent requires a 2 mm overlap. If the Xience Prime stent has to be used, the overlap placement should be done according to its IFU. Such procedures have to be documented accordingly in the eCRF.

## **5.11 Bailout-Staged Procedure**

Planned staged procedures are not allowed in this clinical investigation. If during the intervention it becomes clinically necessary to postpone the treatment, this is regarded as a staged procedure and must be documented in CRF.

# **6 CLINICAL INVESTIGATION PLAN DEVIATIONS**

A Clinical Investigational Plan (CIP) deviation is defined as an instance(s) of failure to follow, intentionally or unintentionally, the requirements of the clinical investigation.

All measures must be undertaken to avoid deviations from the CIP. Deviations from the CIP must

---

be documented in the Case Report Form. Original clinical information should be reserved to report the reasons of plan deviations.

Investigators must also adhere to procedures for reporting CIP deviations to their Ethic Committee (EC) in accordance with their specific EC reporting guidelines and procedures. Under emergency circumstances, deviations from the CIP to protect the rights, safety and well-being of human subjects may proceed without prior approval of the sponsor and the EC. Such deviations shall be documented and reported to the sponsor and the EC as soon as possible.

## 7 Study Participation Status

### 7.1 Status Definitions

**Provisionally enrolled-** A subject who is fully informed about the specifics of the study by the authorized site personnel and provides informed consent by properly signing an informed consent form after confirmation of the initial enrollment criteria.

**Screen failure-** Provisionally enrolled subject who withdraws consent prior to randomization or is unsuitable for randomization following laboratory assessments, pre-procedure electrocardiogram (ECG) or diagnostic angiogram at the index procedure. These subjects will be exited from the study once screen failure is confirmed. Subject informed consent forms will be kept in the site's administrative files.

**Enrolled-** A provisionally enrolled subject who meets all clinical and angiographic eligibility criteria, and has been randomized. These subjects will be followed in accordance with the protocol requirements.

**Study exit-** Early termination of study participation applicable to subjects that have signed an informed consent form.

**Study completion-** A subject who completes all protocol-required study procedures.

### 7.2 Subject Study Exit

Investigators should make every effort to ensure subjects complete all protocol-required procedures, including study follow-up visits. However, subjects may be required to exit the study, despite an investigator's best efforts. Good Clinical Practice (GCP) guidelines describe the need for clear subject exit procedures, to include when and how to exit subjects from the study, as well as to outline the type and timing of the follow-up and data collection for these subjects.

Subjects may be exited from this study in the following limited situations:

- Subject death
- Subject withdrawal of informed consent
- Investigator believes it is in the best medical interest of the subject to discontinue study participation due to safety reasons
- Subject is considered a screen failure or a procedure failure

In any of the situations noted above, data collected up to and including the exit of the subject will be used in data analysis. No data will be collected after the exit of the subject from the study. Study exits are expected and will be taken into consideration during data analysis as described. Additionally, subject attrition has been calculated into the study sample size. Therefore, all subjects exited from the study will be counted toward the randomization goal and will not be replaced. Investigators must document, in subject medical records, the reasons and circumstances for all subject exits.

---

In cases where further participation in the study poses potential risk to the subject, study exit should

be considered. In addition to subject safety, consideration should be given to the scientific validity of the primary endpoints when making decisions concerning subject exit. Study follow-up options and requirements for subjects exiting from the study should be determined and applied to all subjects exiting for similar reasons. Deviations in subject eligibility, as defined in the protocol, should be considered protocol violations and reported to the Institutional Review Board (IRB) or Ethics Committee (EC) immediately upon discovery, in accordance with local regulations.

If a subject cannot continue to participate in the study but the investigator is able to maintain contact with the subject and they have not withdrawn consent to collect further data, then contact should be maintained per the original follow-up schedule and vital status data will be confirmed by the investigator and reported. Identification of vital status will be handled at the investigational site level. Subjects have the right to discontinue from the study at any time or be discontinued at the investigator's discretion.

## **8 DATA REPORTING AND STATISTICAL ANALYSIS**

### **8.1 Determination of Sample Size**

The calculation of the sample size is based on the primary endpoint only: In-stent late lumen (LLL). The trial is based on a non-inferiority hypothesis test, with 2 groups (Orsiro and Xience stents), with a sample allocation ratio 1:1

Since Late Lumen Loss is a quantitative variable and the sample size will be larger enough (at least 200 subjects per group) to invoke the Central Limit Theorem, a student's t-test for independent samples will be used. And since it is a non-inferiority hypothesis, only 1-tail will be tested.

In order to put forward a reasonable LLL hypothesis, data from three different studies is considered. The values are related to in-stent Late Lumen Loss and are displayed in the Table 3.

In-stent Late Lumen Loss (Table 3)							
Product	Study	N	Fup	mean	std. dev.	95% CI	%CV
Xience	Resolute Vs Xience	220	13 mths	0.19	0.40	[0.14,0.24]	211%
	Bioflow II	172	9 mths	0.11	0.29	[0.07,0.15]	264%
	Xience VS Paclitaxel	772	8 mths	0.14	0.41	[0.11,0.17]	293%
Orsiro	Bioflow II	332	9 mths	0.10	0.32	[0.07,0.13]	320%

According to the above data, we first calculate the weighted mean of the control group Xience:  
 Table 4

Product	n	Mean	N*Mean
Xience	220	0.19	41.80
	172	0.11	18.92
	772	0.14	108.08
Orsiro	332	0.10	33.20
Total	1496		202.00

$$\bar{x} = \frac{n_1\bar{x}_1 + n_2\bar{x}_2 + \dots + n_k\bar{x}_k}{n_1 + n_2 + \dots + n_k}.$$

The final weighted mean is 0.14 and assum that both Orsiro and Xience can achieve tha same LLL level.  
 About non-inferiority study: .

$$\begin{aligned} H_0: \mu_{\text{Orsiro}} - \mu_{\text{Xience}} &> \Delta \\ H_A: \mu_{\text{Orsiro}} - \mu_{\text{Xience}} &\leq \Delta \end{aligned}$$

$\mu_{\text{Orsiro}}$  is the LLL level of Orsiro stent at 9 month, and  $\mu_{\text{Xience}}$  is the LLL level of Xience stent at 9 month.

It was assumed  $\mu_{\text{Orsiro}} = \mu_{\text{Xience}} = 0.14$ ; standard deviation for the Late Lumen Loss mean at 9 months is equal for both stents;  $\sigma_{\text{Xience}} = \sigma_{\text{Paclitaxel}} = 0.41$  (the max value for all tests in table 3);  $\Delta = 0.41/3 = 0.137$ ; power of 85%;  $\alpha = 0.025$ ; test: one-sided student's t-test for independent samples; 25% loss for follow-up. Each group of 162 subjects per group, needs to confirm the hypothesis, as well as 216 subjects per group considering a 25% loss for follow-up..

The calculation formula of sample size:

$$n_1 = n_2 = 2 \left[ \frac{(u_\alpha + u_\beta)}{\Delta/\delta} \right]^2 + \frac{1}{4} u_\alpha^2$$

## 8.2 Statistical Analysis

### 8.2.1 The study population is divided into the following categories

- Full analysis set (FAS): The subjects set determined by the intention to treat (ITT) principle refers to the data set constituted by all the subjects participating randomly, using investigational devices and having a baseline curative effect evaluation.
- Per protocol analysis (PPS): Refer to the treatment subpopulation eliminating the serious violation

---

cases.

- Safety analysis set (SS): Refer to the subjects set receiving randomization and minimal one safety evaluation post baseline.

The curative effect evaluation is on the basis of FAS and PPS. All the baseline demographic statistical analysis is on the basis of FAS, and the safety evaluation is on the basis of SS.

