### 4.3.2 Secondary Endpoints

#### 4.3.2.1 Treatment Success Indicator

- 1) Device success, defined as attainment of  $\leq 30\%$  residual stenosis, TIMI=3, of the target lesion using the assigned study stent only.  
Note: Post-dilatation is allowed to achieve device success.
- 2) Lesion success, defined as attainment of  $\leq 30\%$  residual stenosis, TIMI=3, of the target lesion using any percutaneous method.
- 3) Procedure success, defined as attainment of  $\leq 30\%$  residual stenosis, TIMI=3, of the target lesion using the assigned study stent only without occurrence of in-hospital major adverse cardiac events (MACE; composite of all-cause death, Q-wave or non-Q-wave MI, and any clinically-driven TLR).

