##### **4.4.2 Angiographic Inclusion Criteria**

Each target lesion/vessel must meet all of the following angiographic criteria for the subject to be eligible for the trial:

- 1) Target lesion must be in major coronary artery or branch (target vessel).
- 2) Target lesion must have angiographic evidence of  $\geq 70\%$  and  $< 100\%$  stenosis (by operator visual estimate).
- 3) Subject has up to two target lesions (two target lesions in one target vessel, or, for each target vessel, it has one target lesion).
- 4) Target lesion is suitable for drug-eluting stent PCI treatment.
- 5) Target lesion must be  $\leq 36$  mm in length by operator's visual estimate, and can be completely covered by one stent.
- 6) Target vessel must have a reference vessel diameter of 2.25–4.0 mm by operator's visual estimate.
- 7) Target vessel must have a Thrombolysis In Myocardial Infarction (TIMI) flow  $\geq 2$ .

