## 5.2 Enrolment

Subjects are considered enrolled once they signed the informed consent signature form. However, the subjects are eligible for the clinical investigation only after fulfilling the in- and exclusion criteria. The Intention to Treat (ITT) and the CIP population will only be based on eligible subjects.

All target lesions must be treated in one procedure. Planned staged procedures are not allowed. Only Orsiro SES or Xience Prime™ EES may be implanted during the index procedure. There is no restriction in the enrolment of eligible subjects per site.

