### **5.5.1 Baseline Angiography**

Following intracoronary injection of nitroglycerin or isosorbide dinitrate, a baseline angiography of the target vessel must be performed according to the QCA corelab guidelines in at least 2 orthogonal views, presenting the target lesion free of foreshortening or vessel overlap.

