### **5.5.3 Puncture and Predilatation**

The target lesion should be crossed with a 0.014" guide wire. If predilatation is necessary it is recommended to choose following pre-dilation balloons.

2.0 mm for a 2.25 mm vessel  
2.0 mm for a 2.5 mm vessel  
2.5 mm for a 3.0 mm vessel  
3.0 mm for a 3.5 mm vessel  
3.5 mm for a 4.0 mm vessel

Furthermore, the selected pre-dilatation balloon must be a minimum of two millimeters shorter than the nominal length of the Orsiro stent that is planned to be implanted.

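### The full analysis set is called intention-to-treat but requires device use after randomisation, so device and procedure success, if analysed in it, lose randomised subjects who can only be failures

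*Combined protocol and SAP*

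**What the plan says.** Section 8.2.1 says the FAS is determined by the intention-to-treat (ITT) principle and defines it as "all the subjects participating randomly, using investigational devices and having a baseline curative effect evaluation". It then assigns the analyses: "The curative effect evaluation is on the basis of FAS and PPS. All the baseline demographic statistical analysis is on the basis of FAS". The safety set in the same section needs randomisation and one post-baseline safety evaluation, but not device use.

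Two other sections describe the population without a device condition. Section 5.2: "The Intention to Treat (ITT) and the CIP population will only be based on eligible subjects". Section 7.1 defines an enrolled subject as "A provisionally enrolled subject who meets all clinical and angiographic eligibility criteria, and has been randomized". Section 7.2 lists procedure failure among the reasons for exit, says that data up to exit enter the analysis, and counts exited subjects toward the randomisation goal without replacement.

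In section 4.3.2.1, device success requires the assigned stent alone. Procedure success requires a good result "of the target lesion using the assigned study stent only without occurrence of in-hospital major adverse cardiac events". Lesion success allows any percutaneous method. All three are defined by target lesion, and section 4.4.2 allows two: "Subject has up to two target lesions". Section 5.9 has a failed implant recorded as a treatment failure but gives no analysis rule. No section names the analysis set or the denominator for the success indicators.

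**The concern.** A set that follows ITT should not depend on what happens after allocation. Device use does. A subject can be randomised and then have no study stent used, because the lesion cannot be crossed or dilated or because the subject withdraws before any attempt. For device and procedure success this subject is a failure by definition. Dropping the subject removes a failure from the denominator and never a success, so the reported rate can only rise.

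If such subjects are more frequent in one arm, the FAS removes the very failures that make the arms differ. Only the evaluation is described as blinded (synopsis, section 4.2). I infer that the operator knows the assigned stent when deciding whether to go on, so the losses cannot be assumed independent of arm. The FAS baseline tables lose the same subjects.

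**Working it through.** **Order of events.** Section 5.5.1 comes first: "a baseline angiography of the target vessel must be performed according to the QCA corelab guidelines". Randomisation is in 5.5.2. Wire crossing and predilatation follow in 5.5.3: "If predilatation is necessary it is recommended to choose following pre-dilation balloons". Section 5.5.4 forbids opening a stent package before randomisation. Device use is therefore a post-randomisation event, while the baseline angiogram is normally available for everyone randomised.

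**The plan's own figures.** Section 8.1: SD 0.41, margin 0.41/3, true difference 0, one-sided alpha 0.025, power 85%.
- 2 × [(1.960 + 1.036) × 0.41/(0.41/3)]² = 161.6, so 162 per group.
- With the margin rounded to 0.137 and the formula's extra term u²/4 = 0.96: 160.8 + 0.96 = 161.8, again 162.
- 162/0.75 = 216 per group.

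The stated sizes reproduce. I use n = 216 per arm below; the upper limit of 440 in section 4.2 would give 220 and almost the same results.

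**Effect of dropping subjects.** Let S be successes, n subjects randomised in an arm, and k those with no study device used.
- All randomised: S/n. FAS: S/(n − k).
- Difference: S/(n − k) − S/n = (k/n) × S/(n − k), that is, k/n times the FAS rate.
- Per subject at n = 216: 0.90/216 = 0.42 points; 1.00/216 = 0.46 points.

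**Illustrations.** The documents give neither k nor the number of other failures. I assume 4 other failures per arm, which stay in the FAS.

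| k | All randomised | FAS | Rise |
|---|---|---|---|
| 1 | 211/216 = 97.69% | 211/215 = 98.14% | 0.45 |
| 5 | 207/216 = 95.83% | 207/211 = 98.10% | 2.27 |

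Unequal arms, k = 3 against 1:
- All randomised: 209/216 = 96.76% against 211/216 = 97.69%, a difference of 0.93 points.
- FAS: 209/213 = 98.12% against 211/215 = 98.14%, a difference of 0.02 points.

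**Counting by lesion.** FAS membership is decided by subject, so a subject with two lesions takes both out. If every subject has two lesions (432 per arm), one subject leaves and 4 other lesions fail: 426/432 = 98.61% against 426/430 = 99.07%, a rise of 0.46 points. The effect per subject is about the same as with subject counting, not half of it.

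**The case against.** **The FAS may not be the set used, and *using* may be broad.** Both are open. No section ties the success indicators to the FAS, although they are not safety measures and 8.2.1 puts efficacy on the FAS and the per-protocol set. A reader might infer that every failed delivery is dropped. The text does not support that: if *using* covers an attempt, failed deliveries (5.9) stay in as failures, and only subjects with no attempt leave. The conclusion is therefore conditional. But two analysts could report different rates from the same data, which is itself a reason to fix the wording.

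**Section 7.2 points the other way.** It keeps data up to exit for procedure failures and counts these subjects toward the randomisation goal. This favours retaining them, but it names no set or denominator. It leaves 8.2.1 in tension with 7.2 rather than settling the matter.

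**The numbers are small and assumed.** This stands. Sections 4.4.2 and 4.5.2 exclude total occlusions, thrombus and severe tortuosity or calcification, and require lesions suitable for a drug-eluting stent, which limits k. The masking example depends on equal other failures in both arms. Its 0.93-point difference would have a 95% half-width of about 3.1 points even with all subjects counted. The success indicators have no margin or power. Failure to deliver a stent is also a listed adverse event (11.2.1), and the safety set has no device condition.

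**Denominator as a choice.** A rate among subjects in whom the device was tried is a legitimate supportive measure of device performance. It is not an ITT measure and should not carry that label.

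**Conclusion.** The point holds in conditional form. Section 8.2.1 attaches a post-randomisation condition to a set it calls ITT, in conflict with 5.2 and 7.1 and in tension with 7.2. If device and procedure success are analysed in the FAS, each randomised subject with no study device used raises the rate by 0.42 to 0.46 points at 216 per arm (FAS rate 90% to 100%). Under the assumptions above, 1 to 5 such subjects in an arm raise it by 0.45 to 2.27 points. The true total is unknown and probably small.

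Two stronger readings do not follow:
- That the non-inferiority conclusion is compromised. A subject without a study stent has no in-stent late lumen loss to measure under any definition of the FAS. The plan already allows 216 − 162 = 54 subjects per group without an evaluable result, and 162 and 216 do not change.
- That all reported success rates will be too high. This needs both open readings to go one way and at least one affected subject. It also does not extend to lesion success, which allows any method, so that its direction could vary.

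This is worth correcting because two secondary endpoints depend on it and the change is cheap. It does not threaten the trial's main result.

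**What to change.** - In 8.2.1, define the FAS as all randomised subjects, analysed in the assigned arm. Delete the device-use condition and the baseline-evaluation condition; the baseline angiogram precedes randomisation, so little is lost.
- In 5.2, state that ITT means all randomised subjects, including any later found ineligible. Do not tie it to the criteria-met wording of 7.1. Severe calcification that prevents balloon inflation is an exclusion criterion (4.5.2), so a subject with an undilatable lesion could be ruled ineligible afterwards and leave the denominator again. Handle eligibility violations in the per-protocol set.
- Name the FAS for device success and procedure success. State the unit: per target lesion, plus a subject-level rule for two lesions (for example, success only if both succeed). Count any target lesion not treated with the assigned stent as a failure on both endpoints.
- Keep a device-treated set as supportive and define *using* there (attempted or implanted, either arm's device).
- List randomised subjects without a study stent by arm and reason, and make 8.2.1 agree with 7.2.

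**Cost.** No new data: randomisation is in the eCRF (5.5.2) and failed implants are already recorded (5.9). Success rates become slightly less favourable. Subjects who withdraw before any attempt count as failures; the listing shows how many. The change needs a protocol amendment with ethics committee approval before use (10.6).
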